10.2.6 Eighteen -Week administration BPI-SF (Day 125 ± 5)

The Brief Pain Inventory- Short Form questionnaire will be verbally administered to patients by site staff via the telephone. Site staff will schedule a suitable time with the patient to conduct the phone interview and document patient responses.

10.2.7 Twenty-Four Weeks Follow up/ end of study (Day 168 ±7) -VISIT 10

Visit 10 will occur 154 days/22 weeks post completion of NOX66 treatment and consist of the following assessments:

- Physical Examination including vital signs
- Performance Status Assessment (using ECOG performance scale)
- Electrocardiography in triplicate
- Safety blood sampling - Complete Blood Count, Serum Chemistry and Urinalysis
- Biomarker blood sampling – PSA
- Administration of Brief Pain Inventory -Short Form questionnaire
- Concomitant Medication Review
- Adverse Event Review (CTCAE 4.03)
- Tumour Imaging (CT/MRI scan) and Assessment

All patients currently in the study or follow up period, will be asked to re-consent with the revised ICF in order to agree to participate for additional follow up visits (Visit 11 to 16).

For patients who have withdrawn from the study prior to study completion or completed End of Study visit (Visit 10) at the time of this amendment implementation, the investigator or designee will make contact by phone to seek patient willingness to participate in long term follow up and if the patient agrees, a visit will be scheduled for reconsenting.

For Patients who have completed End of Study Visit (Visit 10) at 24 weeks and are unable to be contacted or are > 6 months post EOS, the Investigator or designee at each study site will review medical records from End of Study visit to most recent information available and report on:

- Disease status based on available radiology or other assessments
- Patient Survival information
- Any new anti-cancer treatment after discontinuation of study treatment

10.2.8 Month 9 Long Term Follow up -Visit 11

Visit 11 will occur approximately 3 months after 24 weeks follow up (Visit 10) and consist of the following assessments:

- Performance Status Assessment (using ECOG performance scale)
- Biomarker blood sampling – PSA
- Administration of Brief Pain Inventory -Short Form questionnaire
- Tumour Imaging (CT/MRI/US scan) and Assessment
- Report of any pain medication and any anti-cancer treatment after discontinuation of study treatment

10.2.9 Month 12 Long Term Follow up -Visit 12

Visit 12 will occur approximately 6 months after 24 weeks follow up (Visit 10) and consist of the following assessments:

- Performance Status Assessment (using ECOG performance scale)

- Biomarker blood sampling – PSA
- Administration of Brief Pain Inventory -Short Form questionnaire
- Tumour Imaging (CT/MRI/US scan) and Assessment
- Report of any pain medication and any anti-cancer treatment after discontinuation of study treatment

10.2.10 Month 15 Long Term Follow up -Visit 13

Visit 13 will occur approximately 3 months after the previous visit and consist of the following assessments:

- Biomarker blood sampling – PSA
- Tumour Imaging (CT/MRI/US scan) and Assessment
- Report of any pain medication and any anti-cancer treatment after discontinuation of study treatment

10.2.11 Month 18 Long Term Follow up -Visit 14

Visit 14 will occur approximately 3 months after the previous visit and consist of the following assessments:

- Biomarker blood sampling – PSA
- Tumour Imaging (CT/MRI/US scan) and Assessment
- Report of any pain medication and any anti-cancer treatment after discontinuation of study treatment

10.2.12 Month 21 Long Term Follow up – Visit 15

Visit 15 will occur approximately 3 months after the previous visit and consist of the following assessments:

- Biomarker blood sampling – PSA
- Tumour Imaging (CT/MRI/US scan) and Assessment
- Report of any pain medication and any anti-cancer treatment after discontinuation of study treatment

10.2.13 Month 24 Long Term Follow up -Visit 16

Visit 16 will occur approximately 3 months after the previous visit and consist of the following assessments:

- Biomarker blood sampling – PSA
- Tumour Imaging (CT/MRI/US scan) and Assessment

- Report of any pain medication and any anti-cancer treatment after discontinuation of study treatment

Patients who have disease progression during any of the follow up periods between Visit 10 and Visit 16, will be followed up for survival information by the Investigator or designee via a telephone contact.

All data collected from Visit 11 to 16 will be entered in a paper CRF provided by the Sponsor or delegate.

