Number of subjects planned	Up to 24 patients in 3 idronoxil dose level cohorts of 4 patients (n=12) and an expansion cohort of 12 patients.
Indication / Patient Population	Metastatic castrate-resistant prostate cancer with no remaining standard treatment options. Patients must have at least one metastatic lesion which is amenable to RT.
Study period and duration of treatment	The study will comprise two parts: 1. Treatment and follow up (24 weeks) comprising: 
• NOX66 (Day 1-16)• Palliative Dose Radiation therapy (Day 2-9)• 6-week follow up• 12-week follow up• 24-week follow up 2. Long term follow-up: 
• Ongoing follow up and monitoring of patient to assess long term effects of NOX66 administration and survival including scheduled follow up at 9, 12, 15, 18, 21 & 24 months from treatment commencement date.
Primary study objective	
• To determine the tolerability and toxicity of NOX66 administered in conjunction with palliative radiation therapy
Secondary study objectives	
• To observe any clinical response to treatment of NOX66 in combination with palliative radiation therapy• To observe the effects of NOX66 use on long term (24 months) outcomes for patients

	
 • To document Progression Free Survival (PFS) and Overall Survival (OS) of patients • Exploratory: to measure levels of idronoxil

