10.2 STUDY VISITS

The total study duration per patient will be a minimum of 25 weeks, with continued follow up up to 24 months from the treatment commencement date:

- Screening period: to occur within 2 weeks prior to the scheduled date of treatment commencing
- Treatment and follow up period: up to 24 weeks from the commencement of the first dose of NOX66 and it includes enrolment visit to occur prior to Day 1 of treatment
Long term follow up visits: every 3 months from week 24 for another 18 months.
Observation period (post study follow-up visits): Continued observation of patients beyond 24 months follow up visit, at the discretion of the investigator.

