14 ADVERSE EVENTS REPORTING

Adverse events (AE) or serious adverse events (SAE) reported by the patient or observed by the Investigator will be listed individually on an adverse event form in the CRF. The signs and symptoms, time of onset, duration, treatment (if any), and follow-up procedures (if any) will be reported, and the criteria for assessing causality to study drug and outcome categories should be defined.

Pre-existing conditions or illnesses which are expected to exacerbate or worsen are not considered adverse events and will be accounted for in the patient's medical history.

All adverse events are to be followed up for 30 days following the end of study or until resolution (whichever is sooner).

In order to classify AEs and diseases, preferred terms will be assigned by the Sponsor to the original terms entered on the eCRF using the Medical Dictionary for Regulatory Activities (MedDRA).

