14.2 RESPONSIBILITIES FOR REPORTING

Investigators and the Sponsor are required by regulatory agencies worldwide to report adverse events which involve patients being administered a pharmaceutical product.

All serious adverse events (SAE) occurring from the signing of informed consent until 30 calendar days after last study visit whether related to drug or not, must be reported to the Medical Monitor and appropriate Sponsor contact person within 24 hours of first knowledge of the experience using the appropriate study SAE Report Form. SAEs are to be followed until resolution or stabilisation (with autopsy report if applicable).

Although pregnancy is not a formal SAE, if the study participant or the partner of a study participant becomes pregnant while the study participant is on study, the pregnancy is to be reported on the pregnancy report form via the SAE process.

Deaths and other SAEs occurring > 30 calendar days after last study visit that are deemed 'possibly' or 'probably' related to the study treatment must be reported as SAEs on the SAE Report Form within 1 day of first knowledge of the event by the treating physician or research personnel (with an autopsy report if available).

Deaths occurring > 30 calendar days after last study visit and not attributed to study treatment (e.g., disease progression) need not be reported as SAEs, but simply captured on the appropriate CRF.

The investigative sites will send the SAE report to the Sponsor's Medical Monitor via fax or e-mail and to the Sponsor's pharmacovigilance manager using the contact information below.

Primary Contact [name] [name]	[contact] Email: [contact]
Alternate Contact Study Manager: [name]	Tel: [name]; Fax: [name] Email: [contact]
Pharmacovigilance (DATAPHARM Australia) Manager: [name]	[contact]; [contact] Email: [contact]

Transmission of the SAE Report Form should be confirmed by the site personnel submitting the report. The first report must contain as minimum the study ID, patient number, a description of the event, the name of the investigational product, estimate of causality and the name of the person reporting the event.

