14.2.2 Investigator Reporting of AEs/SAEs/Deaths after Study Discontinuation

Thirty days after completing protocol-specific treatment or study discontinuation, treatment related AEs, SAEs, or deaths determined by the Investigator as treatment related are to be reported directly to the Sponsor.

At the last scheduled study visit, the Investigator should instruct the patient to report to the Investigator any subsequent SAEs that the patient or the patient's personal physician believes could be related to prior study treatment.

SAEs after study discontinuation considered related to study treatment are to be sent to the Sponsor.

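### Visits 11 to 16 schedule no adverse event review, so non-serious late toxicity rests on spontaneous report from Week 24 to month 24, and the end of collection is not defined consistently

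*Combined protocol and SAP*

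**What the plan says.** The synopsis describes the study's second part as "Ongoing follow up and monitoring of patient to assess long term effects of NOX66 administration and survival". It also lists a secondary objective: "To observe the effects of NOX66 use on long term (24 months) outcomes for patients". Section 10.2 sets the schedule: "Long term follow up visits: every 3 months from week 24 for another 18 months".

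The visit lists differ before and after Week 24:

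- **Visits 8, 9 and 10** (10.2.4, 10.2.5, 10.2.7) each list an adverse event review by CTCAE 4.03, with physical examination and safety bloods.
- **Visits 11 and 12** (10.2.8, 10.2.9) list ECOG, PSA, BPI-SF, imaging and "Report of any pain medication and any anti-cancer treatment after discontinuation of study treatment".
- **Visits 13 to 16** (10.2.10 to 10.2.13) list PSA, imaging and that same report.
- **Patients who progress** between Visits 10 and 16 are telephoned for survival (10.2.13).
- **Earlier completers** who cannot be contacted, or who are more than six months past Visit 10, have a chart review of disease status, survival and new anti-cancer treatment (10.2.7).

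For the extended period, the synopsis and section 12.2 plan summaries of overall and progression-free survival, PSA and pain. Adverse events are not named.

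The reporting rules are in section 14. The opening of 14 says "All adverse events are to be followed up for 30 days following the end of study", or until resolution if sooner. Section 14.2 makes SAEs reportable when "occurring from the signing of informed consent until 30 calendar days after last study visit". Section 14.2.2 starts from a third point, "Thirty days after completing protocol-specific treatment or study discontinuation", and has treatment-related events reported directly to the sponsor.

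**The concern.** Safety of NOX66 with palliative radiation is the primary objective (6.1). Section 5.3 says the adverse event profile of this formulation is not fully established and attributes any excess of events to sensitisation to radiation. Late toxicity of the combination is therefore a question the protocol itself raises, and the synopsis presents the long-term part as a place to look at lasting effects. Yet graded review stops at Visit 10.

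What is at stake is how silence would be read. Section 12.2 defines treatment-emergent events by onset on or after the start of therapy, with no upper time limit. An adverse event table built on that definition would pool events sought at scheduled reviews up to Week 24 with events that happened to be mentioned later. After Week 24 there would be no count of patients who were asked. A low late count could mean little toxicity or little enquiry, and the data could not tell these apart.

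The mixed end points add a second problem, because sites could reasonably stop reporting at different times.

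**Working it through.** **1. Length of the period without scheduled review**

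Inputs: Visit 10 at Day 168 ± 7 (10.2.7); six further visits at three-month intervals (10.2); month 24 as the last visit.

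- The plan's own figure: 6 × 3 = 18 months, and 18/24 = 75%. This reproduces.
- In days: one month = 365.25/12 = 30.44 days, so 24 months = 730.5 days.
- Gap from the last scheduled review: (730.5 − 168)/30.44 = 18.5 months, or 77% of 24 months. The ± 7-day window gives 18.3 to 18.7 months.
- If *end of study* means Visit 10 and the 30 days in section 14 are added (Day 198): (730.5 − 198)/30.44 = 17.5 months, or 73%.

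On any reading, the period is about 18 of 24 months.

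**2. The end points side by side**

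- 10.2.7: the heading labels Visit 10 as end of study, although the synopsis counts the long-term visits as part two of the study.
- 14: adverse events are followed up to 30 days after end of study. No sentence says when collection of new non-serious events stops.
- 14.2: SAEs are reportable to 30 days after the last study visit, which could be Visit 10 or Visit 16. Beyond that point only related SAEs must be reported as such. If a site takes Visit 10 as the last visit, SAEs not judged related leave mandatory reporting after Day 198, about month 6.5.
- 14.2.2: the reference point is completion of treatment or study discontinuation. The sentence names treatment-related adverse events without a seriousness limit. The instruction that patients receive at their last visit covers SAEs only.

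**3. What asking would add**

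The documents give no late-toxicity rate, so the rates here are assumptions. Up to 24 patients are planned. The figure of 12 assessable patients is also an assumption, chosen to show the effect of attrition. The chance of at least one case among n patients who are asked is 1 − (1 − p)^n:

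- p = 5%: 1 − 0.95^24 = 71%; 1 − 0.95^12 = 46%.
- p = 10%: 1 − 0.90^24 = 92%; 1 − 0.90^12 = 72%.

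Conversely, if n patients are asked and none has an event, the one-sided 95% upper limit for the rate is 1 − 0.05^(1/n): 11.7% for n = 24 and 22.1% for n = 12. Without a known number of patients asked, no such limit can be given.

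**The case against.** The strongest reply is that late events have a route into the record. The opening of section 14 has events reported by the patient or observed by the investigator listed in the CRF, with no end date in that sentence, and 14.2.2 covers treatment-related events whether serious or not. A reader might infer that late non-serious toxicity goes unrecorded, or that only serious events would be captured. The documents do not support either inference. Nor does 14.2.2 clearly close reporting at 30 days: its heading concerns the time after discontinuation, and the more natural reading is that direct reporting to the sponsor starts then. What remains is that the route is passive. It depends on a relatedness judgement at visits where no toxicity question is listed, and the paper CRF for Visits 11 to 16 (10.2.13) is not said to carry an adverse event page.

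The second reply is attrition, and it stands. A reader might take 92% as the size of the loss, but that needs all 24 patients assessable. Eligibility asks for a life expectancy of only 24 weeks, progressors move to telephone contact about survival, and some earlier completers have chart review only. Some late events would also surface spontaneously, so the figures in the working show what asking could find, not what the plan would miss.

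The third reply is scope. NOX66 is given for up to 16 days, graded review runs to Week 24, the extended summary names only survival, progression, PSA and pain, and no 24-month safety statement is announced. That is a defensible design, but it does not fit the synopsis phrase about long-term effects of NOX66. One of the two has to change.

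**Conclusion.** The point holds as a gap in active collection and an inconsistency in definitions. None of Visits 11 to 16 schedules an adverse event review, for about 18 of 24 months (73% to 77% of follow-up by exact days, depending on where collection is taken to end). Non-serious late toxicity in that period rests on spontaneous report, is not graded on schedule and has no denominator, so its absence could not be interpreted. The conclusion about the visits rests on the visit lists alone. The 46% to 92% range rests on assumed rates of 5% to 10% and on 12 to 24 assessable patients.

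A reader might also infer that dose selection is compromised. It is not: escalation uses discontinuations up to Visit 7, and the expansion dose uses Week 6 data (10.2.14, 13.2), both within the period of scheduled review. What is affected is any statement about safety out to 24 months. The correction is cheap and worth making.

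**What to change.** 1. Add to Visits 11 to 16 (10.2.8 to 10.2.13), and to the long-term paper CRF, an adverse event review by CTCAE v4.03. Limit it to events in the irradiated field or judged related to NOX66 or the combination.
2. In the synopsis and section 12.2, add these events to the extended-period summary, with the number of patients assessed at each visit, and show them separately from events up to Week 24.
3. Use one defined end of adverse event collection in 14, 14.2 and 14.2.2, for example 30 days after Visit 16 or the last contact. Bring the heading of 10.2.7 into line with it.

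If the sponsor does not want this, the alternative is to restate the long-term aim in the synopsis as survival, progression, PSA and pain only, and to make no 24-month safety statement. Item 3 is needed either way.

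The cost is a few minutes at visits already scheduled and one CRF page. Patients followed only by telephone or chart review will contribute less, which is why the number assessed has to be reported.

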10.2.14 Cohort Allocation and Dose Escalation

[figure not shown]
This study will enrol up to 24 patients across three dose levels of NOX66. Dose cohort assignment will be sequential and dose escalation decisions will be based on patients who experience adverse events directly related to NOX66 treatment and discontinued as described below and outlined in Figure 2.

Dose escalation and decision rules are as follows:

- **Patients 1-4 (Dose Cohort 1)** will be prescribed NOX66 400mg.
- **Patients 5-8 (Dose Cohort 2):** Once fourth patient in Cohort 1 has completed treatment (Visit 7), the dose of NOX66 for next cohort, patients 5-8, will be as determined as follows, based on the number of discontinuations due to NOX66 related adverse events:
 - If no patients discontinue treatment, NOX66 dose will be increased to 800mg
 - If one patient discontinues treatment, NOX66 dose will remain at 400mg
 - If more than one patient discontinues treatment, there will be no further recruitment to the study until scans from WEEK 6 are assessed for disease status
- **Patients 9-12 (Dose Cohort 3):** Once the eighth patient in Cohort 2 has completed treatment (Visit 7), the dose of NOX66 for next cohort, patients 9-12, will be as determined as follows, based on the number of discontinuations due to NOX66 related adverse events:
 - If no patients in Dose Cohort 2 discontinue treatment, NOX66 dose will be increased (from 400mg to 800mg or from 800mg to 1200mg)
 - If one patient in Dose Cohort 2 discontinues treatment, NOX66 dose will remain at the same dose (400mg or 800mg)
 - If more than one patient in Dose Cohort 2 discontinues treatment, dose will be reduced (from 800mg to 400mg) or, if dose has remained at 400mg, there will be no further recruitment to the study until scans at WEEK 6 are assessed for disease status.

Following the review of all accumulated safety data, disease status and treatment efficacy signals from scans assessed per RECIST 1.1 criteria and preliminary pain response at WEEK 6 for all patients, the Study Steering Committee will determine the dose at which to continue treatment for the expansion patient Cohort 4 in the study. A further 12 patients will be recruited at this dose level.

Figure 2: Dose Escalation and Dose Expansion Schema

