9.4 TREATMENT DOSE MODIFICATIONS AND TREATMENT CYCLE DELAY

9.4.1 NOX66

Any patient who experiences toxicity > Grade 2 related to NOX66 will have the idronoxil treatment withheld for 1 day and then resume on the next lower dosage (1200 mg reduced to 800 mg; 800 mg reduced to 400 mg; 400 mg daily reduced to 400 mg every 2nd day) for the remainder of the treatment period.

If toxicity > Grade 2 persists following reduction of dose, the idronoxil treatment will cease immediately for the remainder of the treatment period, although the patient may remain in the study.

There will be no dose modification of NOX66 on the basis of body weight.

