10 STUDY PROCEDURES

10.1 OUTCOME MEASURES

The outcome measures supporting the primary objective of this study are:

- Number of events of > Grade 2 toxicity (as scored by CTCv4.03)
- Number of events of > Grade 2 toxicity considered by the investigator and / or the Sponsor as causally related to the use of NOX66 (as scored by CTCv4.03)
- The overall number of adverse events considered by the investigator and / or the Sponsor as causally related to the use of NOX66
- Incidence of dose limiting toxicities (DLT) and or maximum tolerated dose (MTD) of NOX66

The outcome measures supporting the secondary objectives of this study are:

- Where target (measurable) lesions have been identified:
 - a. Change intumour size of irradiated lesions according to RECIST1.1 criteria, as assessed by central review and by the investigator based on CT/MRI scan
 - b. Change in tumour size of target non-irradiated lesions according to RECIST1.1 criteria, as assessed by central review and by the investigator based on CT/MRI scan
 - c. Observation of change from baseline in Non-target lesions according to RECIST 1.1 criteria
- For all patients – overall assessment of change in disease state by an independent Radiation Oncology Expert Committee
- Change from baseline in pain score based on responses to BPI-SF
- Observation of change from baseline in PSA levels
- Assessment of patient via physical exam and ECOG Score

- Plasma level of idronoxil post treatment (immediate and long term (at 6 weeks))
- Duration of tumour progression free state from study treatment start date
- Duration of survival from study treatment start date

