Patient may be contacted by telephone after enrolment as a reminder to start NOX66 administration day prior to attending clinic for radiation therapy.

10.2.3 Treatment Cycle (Days 1-16) - Visits 2 to 7

Treatment will Commence on Day 1 of the Study Visit Schedule (Table 1) and the procedures for Treatment Visits are listed below in Table 1.

Overall, the patient will attend the clinic on 7 days during the Treatment Cycle.

During the Treatment Cycle, the patient will receive treatment of:

- NOX66 (Dose dependent on treatment cohort) for 13 up to 16 consecutive days (Days 1-16), inclusive of weekends and public holidays.
- Palliative radiation therapy (20Gy Dose) in five fractions over 8 days commencing on Day 2 to Day 9. Radiation therapy **not given** on weekends and public holidays.

Table 1. Schedule of Assessments: TREATMENT CYCLE

Period	Pre-RT		RT									Post RT					EoT ³
	D0 (-7)	D 1	D 2	D 3	D 4	D 5	D 6	D 7	D 8	D 9	D 10	D 11	D 12	D 13	D 14	D 15	D 16+1
VISITS	V1 ¹		V2	V3 - V6 ²													V7
NOX66 (Self-administration)		X	X	X	X	X	X	X	X	X	X	X	X	X	X	X	X ⁴
Radiation therapy			X	X													
Physical exam			X														X
ECG																	X
Vital Signs			X														X
Complete Blood Count																	X
Serum chemistry																	X
Urinalysis																	X
Biomarker ⁵	X																X
BPI-SF ⁶ Questionnaire																	X
Concomitant medications/ Adverse Event ⁷ review			X	X													X
Dispense NOX66	X																
Return NOX66																	X

¹Enrolment-Visit to occur after eligibility confirmation (Screening) and prior to V2, to receive NOX66 and education on self-administration

² Patient attend clinic for 5 days in an 8-day period to receive RT. Patient will not attend clinic on days where RT is not conducted

³ End of Treatment (EoT) visit to occur Day following last dose of NOX66

⁴NOX66 dosing continues to Day 16 if there has been (weekend and public holiday -up to 3 days) interruption in RT in Treatment Cycle.

⁵ Biomarkers include idronoxil

⁶ Brief Pain Inventory-Short Form (1991)

⁷ Adverse Event (AE) assessed by Investigator using the NCI CTCAE v4.03 scoring system

10.2.4 Six-Week Follow up (Day 43 ± 5) - Visit 8

Visit 8 will occur 28 days/4 weeks post completion of NOX66 treatment and consist of the following assessments:

- Physical Examination including vital signs
- Performance Status Assessment (using ECOG performance scale)

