Safety Analysis: The safety will be assessed through the analysis of the reported incidence of treatment emergent AEs, including SAEs, dose-limiting toxicities, AEs leading to withdrawal, events of at least CTCAE Version 4.03 Grade 3 in severity, and AEs related to study treatment. Treatment emergent AEs are those with an onset on or after the initiation of therapy. Other safety endpoints include laboratory results, physical examinations, vital signs, and changes in ECOG status. A copy of CTCAE Version 4.03 scoring system may be downloaded from:

http://evs.nci.nih.gov/ftp1/CTCAE/CTCAE_4.03_2010-06-14_QuickReference_8.5x11.pdf.

The adverse events will be summarized by MedDRA coding terms, System Organ Class (SOC), and preferred term for all treated patients and by dose cohort. The AEs will also be tabulated by maximum severity and maximum relationship to study drug where applicable. The number and percent of patients experiencing dose-limiting toxicities will be summarized by dose cohort, by DLT, and system organ class for all treated patients. Other safety endpoints, which include change from baseline in laboratory results and vital signs, and shifts in physical examinations, will be summarized throughout the study by visit for each dose level for all treated patients.

Concomitant medications: are to be listed for all patients.

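### Section 10.2.14 escalates on NOX66-related discontinuations alone, so a patient who is dose-reduced for a related > Grade 2 toxicity and finishes, or whose laboratory or QTc toxicity is first found at Visit 7, counts as zero

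*Combined protocol and SAP*

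**What the plan says.** Section 10.2.14 fixes the basis for escalation: "dose escalation decisions will be based on patients who experience adverse events directly related to NOX66 treatment and discontinued as described below". After each of the first two cohorts of four, the next dose depends on the number of discontinuations due to NOX66-related events. None means increase, one means stay, and more than one means pause recruitment or reduce. For the step to Cohort 3: "If no patients in Dose Cohort 2 discontinue treatment, NOX66 dose will be increased (from 400mg to 800mg or from 800mg to 1200mg)". Neither toxicity grade nor DLT appears in the rule.

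Section 9.4.1 handles a related toxicity above Grade 2 by a one-day hold, after which the patient is to "resume on the next lower dosage (1200 mg reduced to 800 mg; 800 mg reduced to 400 mg" (and 400 mg daily becomes 400 mg every second day). Stopping is the next step: "If toxicity > Grade 2 persists following reduction of dose, the idronoxil treatment will cease immediately".

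In Table 1 (10.2.3), blood count, chemistry, urinalysis and ECG within the treatment cycle are scheduled only at Visit 7. Its footnote places that visit after dosing: "End of Treatment (EoT) visit to occur Day following last dose of NOX66".

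The primary outcomes in 10.1 include "Number of events of > Grade 2 toxicity (as scored by CTCv4.03)", the NOX66-related subset of those events, and "Incidence of dose limiting toxicities (DLT) and or maximum tolerated dose (MTD) of NOX66". Section 12.2 adds: "The number and percent of patients experiencing dose-limiting toxicities will be summarized by dose cohort". The text provided does not define a DLT or connect it to 10.2.14.

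Section 13.2 has related events of Grade 2 or above reported to the SSC at once, and has the SSC determine escalation after the cohort's last Visit 7.

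**The concern.** The rule and the dose-modification section work against each other. Section 9.4.1 keeps a patient with a related > Grade 2 toxicity on treatment at a lower dose. Section 10.2.14 then treats that patient as having tolerated the cohort dose, because nobody stopped. An abnormality first detected the day after the last dose has the same result, since no treatment is left to stop.

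At stake is the only numerical escalation criterion in the protocol text. It can direct an increase on the strength of patients who could not stay on the dose being judged. It is also blind to part of what 10.1 makes primary. The missing DLT definition adds to this, because DLT incidence by cohort cannot be reported reproducibly without one.

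**Working it through.** **The plan's own figure.** 3 cohorts × 4 + 12 in the expansion = 24, as stated in the synopsis. The plan gives no error rate, power or target toxicity rate, so there is nothing further to reproduce.

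**What enters the count (from the text alone).**

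| Course of a related > Grade 2 toxicity | Source | Count in 10.2.14 |
|---|---|---|
| Persists after reduction, NOX66 stopped | 9.4.1 | 1 |
| Intolerable event or investigator judgement, treatment stopped | 8.4 | 1 |
| Stopped by investigator or SSC decision | 3.4, 13.2 | 1 |
| Reduced, finishes on the lower dose | 9.4.1 | 0 |
| Laboratory or QTc finding first seen at Visit 7 | Table 1 | 0 |

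**Worked case.** Suppose all four Cohort 2 patients (800 mg) have a related Grade 3 event on Day 4, are held on Day 5 and finish on 400 mg.

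- 13-day course: 4×800 + 0 + 8×400 = 6400 mg of 13×800 = 10400 mg, or 61.5%.
- 16-day course: 4×800 + 0 + 11×400 = 7600 mg of 16×800 = 12800 mg, or 59.4%.
- Discontinuations: 0 of 4. The rule reads 1200 mg, and 1200/400 = 3 times the dose on which all four finished.

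This result needs no assumed rate.

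**Illustrative probabilities.** The documents give no toxicity rate for NOX66 with radiation therapy, so both inputs are assumptions. Let t be the per-patient chance of a related > Grade 2 toxicity by Visit 7, and q the share of those patients who discontinue. Patients are taken as independent, and discontinuations are taken to occur only among affected patients.

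- As written, the count is Bin(4, tq), and P(escalate) = (1 − tq)^4.
- Amended (see the fix), the count is Bin(4, t), with P(escalate) = (1 − t)^4, P(stay) = 4t(1 − t)^3, and P(>1) the remainder.
- Example, t = 0.20: as written with q = 0.25, 0.95^4 = 0.815. Amended: 0.8^4 = 0.410 escalate, 4×0.2×0.512 = 0.410 stay, and 0.181 for >1.

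| t | Written, escalate: q=0 | q=0.25 | q=0.50 | Amended: escalate | stay | >1 |
|---|---|---|---|---|---|---|
| 10% | 100% | 90% | 81% | 66% | 29% | 5% |
| 20% | 100% | 81% | 66% | 41% | 41% | 18% |
| 33% | 100% | 71% | 49% | 20% | 40% | 40% |
| 50% | 100% | 59% | 32% | 6% | 25% | 69% |

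At q = 1 the two rules coincide. None of these figures allows for SSC intervention.

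**If NOX66 is as benign as hoped.** Section 5.3 reports no adverse events of Grade 2 or higher with intravenous and oral idronoxil, and 4.4 mentions over 400 patients. Reading this as 0 of 400 (an assumption) gives an upper bound of about 3/400 = 0.75%. The amended rule then reads escalate 0.9925^4 = 97%, stay 3%, >1 of 4 0.03%.

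**The case against.** The strongest objection is that 10.2.14 does not operate alone. Each related Grade 2+ event goes to the SSC immediately for a decision on the patient and the study. Section 3.4 gives the SSC discretion over the study, and the synopsis and 13.2 both say that it determines escalation. In the four-of-four case the SSC would have heard of every event, and a related Grade 2+ finding at Visit 7 would also reach it before the decision. This stands as mitigation. It does not close the gap, because that review has no stated toxicity threshold while 10.2.14 says that the dose will go up.

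A reader might infer that related > Grade 2 toxicities never enter the count. The text does not support that: 9.4.1, 8.4, 3.4 and 13.2 all offer routes to stopping, and a patient who stops because of a related event is counted.

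Timing is a fair objection. Section 10.2.7 provides for patients who are already past Visit 10, some by more than six months, so the early dose decisions may be closed; the text does not say. The expansion dose is in any case set on all accumulated safety data, not on this count.

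The amendment also has a real price. At t = 33% it reaches the >1 of 4 branch 40% of the time. Attribution would drive many of those results, since 5.3 expects excess toxicity, such as fatigue above Grade 2, to come from the combination and to reflect greater efficacy.

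Finally, the proposed DLT is close to an outcome already in 10.1. It differs in counting patients rather than events, in having a fixed window, and in including related discontinuations.

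**Conclusion.** The point holds as a statement about the written rule. From the text alone, four of four patients with a related > Grade 2 toxicity can produce a count of zero and an instruction to increase the dose. In the worked case the increase is to three times the dose on which they finished.

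A reader might go further and infer that unsafe escalation is inevitable. The documents do not support this, because the SSC sees the events and takes the decision. Nor should the as-written versus amended probabilities be read as estimates: they depend on an assumed t and on the assumed share of affected patients who discontinue.

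The conclusion rests on two readings. The first is that a patient who resumes at a lower dose has not discontinued, which is how 9.4.1 separates resuming from ceasing. The second is that Figure 2, which is not shown, adds no further criterion. The change should be made, but SSC oversight and the possibility that the cohort doses are already assigned limit its urgency.

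**What to change.** For any escalation decision still open, amend 10.2.14 so that a patient counts once in the existing 0 / 1 / >1 of 4 rule if, by Visit 7, he has either (a) a NOX66-related > Grade 2 toxicity, whether clinical, laboratory or QTc, including one managed by reduction under 9.4.1; or (b) a discontinuation due to a NOX66-related adverse event of any grade. Use the same definition for DLT in 10.1 and 12.2. The threshold matches 9.4.1 and 10.1; the synopsis, which uses Grade 2 or above, should be aligned.

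If the cohort doses have already been assigned, apply the definition to the expansion-dose review if that is still open, and to the DLT summary. State that it was set after the earlier decisions.

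The change needs one amended rule and one definition, with no added visit or procedure. Its cost is slower escalation and, in the >1 of 4 branch, either a recruitment pause until the Week 6 scans (after Cohort 1, or in Cohort 2 if still at 400 mg) or a reduction from 800 mg to 400 mg. An event wrongly attributed to NOX66 could trigger either.
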